
3.9.2.2 Liver function parameters

Liver function parameters of interest for alpelisib are total bilirubin (TBIL), ALT, AST and alkaline phosphatase (ALP).

The number (%) of patients with worst post-baseline values (maximum post-baseline values) as per Novartis Liver Toxicity guidelines will be summarized:

- ALT or AST > 3xULN
- ALT or AST > 5xULN
- ALT or AST > 10xULN
- ALT or AST > 20xULN
- ALP > 1.5xULN
- TBL > 1.5xULN
- TBL > 2xULN
- ALT or AST > 3xULN & TBL > 2xULN (without time window)
- ALT or AST > 3xULN & TBL > 2xULN & ALP < 2xULN (without time window)*

*Potential Hy's Law events (candidates) are defined as those patients with AST or ALT > 3xULN and TBL > 2xULN and ALP < 2xULN at any visit during the on-treatment period.

A figure displaying time course of hepatic function tests (ALT, AST, TBL, ALP) in patients with potential Hy's law cases will be displayed.

Additional categories may be added to the above list based on any updates to the internal guidelines on collection, analysis, and presentation of liver safety data.

For lab events the censoring date will be the date of the last scheduled/unscheduled lab assessment with a non-missing value for the lab parameter of interest that was collected prior to the time of occurrence of the censoring reason.

3.9.3 Vital signs

Vital signs assessments are performed in order to characterize basic body function. The parameters expected to be collected include: height, weight, body temperature, heart rate, and systolic and diastolic blood pressure.

The criteria for clinically notable abnormalities are defined as follows:

Clinically notable elevated values

- Systolic BP: ≥ 180 mmHg and an increase ≥ 20 mmHg from baseline
- Diastolic BP: ≥ 105 mmHg and an increase ≥ 15 mmHg from baseline.
- Body temperature: $\geq 39.1^{\circ}\text{C}$
- Pulse rate: $>=100$ and increase from baseline of $>25\%$
- Weight: Increase $\geq 10\%$ from baseline

Clinically notable below normal values

- Systolic BP: ≤ 90 mmHg and a decrease ≥ 20 mmHg from baseline
- Diastolic BP: ≤ 50 mmHg and a decrease ≥ 15 mmHg from baseline
- Pulse rate: $<=50$ and decrease from baseline of $>25\%$
- Weight: Decrease $\geq 10\%$ from baseline

The following summaries will be produced for each vital sign parameter:

- Number and percentage of patients with at least one post-baseline vital sign abnormality (in both directions, i.e. both elevated and below normal values).

In addition, the following two listings will be produced by treatment arm:

- Patients with clinically notable vital sign abnormalities.
- All vital sign assessments will be listed by patient and vital sign parameter.

In both listings, the clinically notable values will be flagged and also the assessments collected later than 30 days after the last treatment date will be flagged.

3.9.4 ECG

All analyses of ECG data will be based on the average of all available replicate ECGs assessed by the central reader at each scheduled time point for each patient. ECG data will be summarized by presenting summary statistics of the raw data and change from baseline by treatment arm and time point. The following parameters will be assessed: QT, QTcF, PR, and QRS intervals in ms, heart rate (bpm), and the overall interpretation if clinically significant abnormalities are present. The number and percentage of patients with notable abnormalities will be summarized. Individual listings will be provided by subject.

Table 3-8 Clinically notable ECG values

ECG parameter (unit)	Clinically notable criteria
QT, QTcF (ms)	New value of > 450 and ≤ 480 ms New value of > 480 and ≤ 500 ms New value of > 500 ms Increase from Baseline > 30 to ≤ 60 ms Increase from Baseline > 60 ms
PR duration (ms)	Increase $> 25\%$ from baseline and to PR duration > 200 New value of > 200 ms
QRS duration (ms)	Increase $> 25\%$ from baseline and to QRS duration > 120 ms New value of > 120 ms
Heart Rate (bpm)	Decrease from Baseline of $> 25\%$ and to a value < 50 bpm Increase from Baseline of $> 25\%$ and to a value > 100 bpm

A newly occurring ECG abnormality is defined as an abnormal post-baseline ECG finding that

is not present at Baseline. Baseline is defined as the last ECG measurements taken during the screening phase. The percentage of patients having notable ECG interval values is based on the number of patients at risk for the change with a value at baseline and post-baseline.

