14. Patient has a known history of Human Immunodeficiency Virus (HIV) infection (testing not mandatory)
15. Patient has any other concurrent severe and/or uncontrolled medical condition that would, in the investigator's judgment, contraindicate patient participation in the clinical study (e.g. chronic active hepatitis, severe hepatic impairment, etc.)
16. Patient has currently documented pneumonitis (chest CT scan performed at baseline for the purpose of tumor assessment should be reviewed to confirm that there are no relevant pulmonary complications present).
17. Patient has clinically significant, uncontrolled heart disease and/or recent cardiac events including any of the following:
 - History of angina pectoris, coronary artery bypass graft (CABG), symptomatic pericarditis, or myocardial infarction within 12 months prior to the start of study treatment
 - History of documented congestive heart failure (New York Heart Association functional classification III-IV)
 - Documented cardiomyopathy
 - Patient has a Left Ventricular Ejection Fraction (LVEF) $<$ 50% as determined by MUGA scan or ECHO
 - History of any cardiac arrhythmias, (e.g. ventricular tachycardia), complete left bundle branch block, high grade AV block (e.g. bifascicular block, Mobitz type II and third degree AV block), supraventricular, nodal arrhythmias, or conduction abnormality in the previous 12 months.

- Uncontrolled hypertension defined by a Systolic Blood Pressure (SBP) \geq 160 mmHg and/or Diastolic Blood Pressure (DBP) \geq 100 mm Hg, with or without anti-hypertensive medication. Initiation or adjustment of antihypertensive medication(s) is allowed prior to screening.
- Long QT syndrome, family history of idiopathic sudden death or congenital long QT syndrome, or any of the following:
 - Risk factors for Torsades de Pointe (TdP) including uncorrected hypokalemia or hypomagnesemia, history of cardiac failure, or history of clinically significant/symptomatic bradycardia
 - Concomitant medication(s) with a known risk to prolong the QT interval and/or known to cause TdP that cannot be discontinued or replaced by safe alternative medication
 - Bradycardia (heart rate $<$ 50 at rest), by ECG or pulse.
 - On screening, inability to determine the QTcF interval on the ECG (i.e.: unreadable or not interpretable) or corrected QT (QTcF) $>$ 450 msec for males and $>$ 460 msec for females (using Fridericia's correction). All as determined by screening ECG (mean of triplicate ECGs).

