7.2.2.7 Cardiac assessments

7.2.2.7.1 Electrocardiogram (ECG)

A standard 12 lead ECG will be performed after the patient has been resting for 5-10 min prior to each time point indicated in [Table 7-5](#). At screening, triplicate ECGs should be taken approximately 2 minutes apart. The combined QTcF values will be averaged to provide a single

[REDACTED]

baseline value for each patient. This averaged value will be documented in the ECG section of the CRF.

The interpretation of the tracing must be made by a qualified physician and documented in the ECG section of the CRF. Each ECG tracing should be labeled with the study number, patient initials (if permitted by local regulations), Subject No, date, and kept in the source documents at the study site. Clinically significant abnormalities present when the patient signed informed consent should be reported on the Medical History CRF page. Clinically significant findings must be discussed with the Novartis Medical Monitor prior to enrolling the patient in the study. New or worsened clinically significant findings occurring after informed consent must be recorded on the adverse events CRF page.

Table 7-5 Local ECG collection plan

Cycle	Patients	Day	Time	ECG Type
Screening	All	Day -28 to -1	Anytime	TriPLICATE 12 Lead
Cycle 1	All	Day 1	Pre-dose ¹	12 Lead
Cycle 1	All ¹	Day 15	2h Post-dose ± 30 min ¹	12 Lead
Every 2 cycles until 36 months, then change to as clinically indicated	All	Day 1	Pre-dose ¹	12 Lead
EOT	All	N/A	Anytime	12 Lead
Unscheduled sample ²			Anytime	12 Lead

¹ ECG assessments are to be done **prior** to PK sampling
² If an unscheduled ECG is performed for safety reasons, it is recommended to collect a time-matched PK sample and record the time and date of the last study drug intake to determine the drug exposure

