2.1.8 Baseline

Baseline is the result of an investigation describing the “true” uninfluenced state of the patient, defined as the period from the date of signing any informed consent document to the start date of study treatment or the date of randomization. Assessments, specified to be collected post-dose on the first date of treatment are not considered as baseline values.

For efficacy evaluations, the last non-missing assessment, including unscheduled assessments on or before the date of randomization is taken as “baseline” value or “baseline” assessment.

For RECIST-based endpoints including PFS, ORR, CBR, [REDACTED] a window of 7 days from the start of study treatment will be allowed, i.e. the

investigator/BIRC-reported responses will be maintained and baseline considered valid if the baseline assessment is within 7 days of treatment start date. In the context of baseline definition, the efficacy evaluations also include ECOG performance status and PRO. If a patient has 2 ECOG PS (or PRO) values at the same date, the worst ECOG PS value will be taken as 'baseline'. [REDACTED]

For safety evaluations (i.e. laboratory assessments, ECGs and vital signs), the last available assessment, including unscheduled assessments on or before the start date of study treatment (Cycle 1 Day 1) as described in [Section 2.1.4](#) is taken as "baseline" value or "baseline" assessment.

In rare cases, where multiple safety measurements meet the baseline definition, with no further flag or label that can identify the chronological order, then the following rule should be applied: If values are from central and local laboratories, the value from central assessment should be considered as baseline. If multiple values are from the same laboratory (local or central) or collected for ECGs or vital signs, then the last value should be considered as baseline.

If patients have no value as defined above, the baseline result will be missing.

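### SAP 3.9.4 names a central ECG reader that the readable protocol does not set up, and SAP 2.1.8 picks a different QTcF baseline from SAP 3.9.4 and the protocol

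*SAP*

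**What the plan says.** **Source of the data.** SAP 3.9.4 rests all ECG analyses on the "average of all available replicate ECGs assessed by the central reader at each scheduled time point". In the protocol, Table 7-5 is headed "Local ECG collection plan". It lists a triplicate 12-lead ECG at screening and one 12-lead ECG at each later scheduled time: Cycle 1 Day 1 pre-dose, Cycle 1 Day 15 two hours post-dose, every two cycles on Day 1, and end of treatment. On reading, protocol 7.2.2.7.1 states: "The interpretation of the tracing must be made by a qualified physician and documented in the ECG section of the CRF". The tracings stay in source documents at the site.

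**Baseline.** Three rules bear on it.
- Protocol 7.2.2.7.1: "At screening, triplicate ECGs should be taken approximately 2 minutes apart". It continues "The combined QTcF values will be averaged to provide a single" baseline value, which is entered in the CRF. Exclusion criterion 17 (protocol 5.3) uses the same mean for eligibility.
- SAP 2.1.8, which names ECGs among the safety evaluations, takes "the last available assessment, including unscheduled assessments on or before the start date of study treatment".
- SAP 3.9.4: "Baseline is defined as the last ECG measurements taken during the screening phase".

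**Use.** SAP Table 3-8 counts patients with QTcF increases from baseline of more than 30 up to 60 ms, and of more than 60 ms. It also has percentage-change categories for PR, QRS and heart rate.

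**The concern.** A programmer who follows SAP 3.9.4 literally would look for centrally read replicates at every visit. The readable protocol does not create such a dataset.

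The same programmer has two SAP rules for the ECG baseline that point to different visits, and the SAP does not say which prevails. The change-from-baseline categories in Table 3-8 depend directly on that choice. QT is a followed safety question in this trial: Table 7-5 includes a post-dose ECG in all patients on Cycle 1 Day 15. An unsettled baseline leaves those counts open to a programming choice, and they may not match changes calculated from the baseline that the protocol records in the CRF.

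**Working it through.** The plan gives no figure to reproduce. The check is a comparison of texts, followed by an illustration of size.

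**Step 1: source.**

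| Item | SAP 3.9.4 | Protocol 7.2.2.7.1 and Table 7-5 |
|---|---|---|
| Reader | Central | Qualified physician, result in the CRF, tracing kept at site |
| Replicates | Averaged at each scheduled time point | Triplicate at screening, one tracing afterwards |

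The central data flows in protocol 9.3 and 9.4 name laboratory, PK, imaging, IRT and PRO data. Their readable text does not name ECGs.

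**Step 2: baseline.** Table 7-5 schedules a pre-dose ECG on Cycle 1 Day 1 for all patients.

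| Rule | ECG selected in a patient who follows the schedule |
|---|---|
| Protocol 7.2.2.7.1 (QTcF) | Mean of the screening triplicate |
| SAP 3.9.4 | Last measurements of the screening phase |
| SAP 2.1.8 | Single Cycle 1 Day 1 pre-dose tracing |

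SAP 2.1.8 therefore conflicts with SAP 3.9.4 on the visit, and with the protocol on both the visit and the averaging.

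**Step 3: illustration of size.** Let s be the within-patient SD of one QTcF reading. The documents give no value, so s is an assumption, varied from 8 to 15 ms. Assume no true QTcF change, normal and independent errors, and one post-baseline tracing.

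- Triplicate-mean baseline: SD of change = s × √(1 + 1/3) = 1.155s.
- Single-tracing baseline: SD of change = s × √2 = 1.414s.
- Ratio: 1.414 / 1.155 = 1.22, so the single baseline gives a 22% larger SD.
- Chance of a false increase above T ms = 1 − Φ(T / SD of change).

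Worked case, s = 10 ms and T = 30 ms: 30/11.55 = 2.60 gives 0.47%; 30/14.14 = 2.12 gives 1.70%.

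| s (ms) | > 30 ms, triplicate mean | > 30 ms, single tracing | > 60 ms, triplicate mean | > 60 ms, single tracing |
|---|---|---|---|---|
| 8 | 0.06% | 0.40% | < 0.001% | < 0.001% |
| 10 | 0.47% | 1.70% | < 0.001% | 0.001% |
| 12 | 1.5% | 3.9% | 0.001% | 0.02% |
| 15 | 4.2% | 7.9% | 0.03% | 0.23% |

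These are chances per ECG. The chance of at least one such value per patient is higher, because patients have several post-baseline ECGs.

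The independence assumption favours the triplicate. Tracings taken about two minutes apart share any day-to-day variation, and averaging does not remove that part. The 22% is therefore the largest gain that this model allows.

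**The case against.** The averaging rule in SAP 3.9.4 works on the data as collected: it averages whatever replicates are available, so it gives the triplicate mean at screening and the single value afterwards. That stands. A reader might infer that the trial collects no replicates at all. It does collect them, at screening in every patient.

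A reader might also infer that SAP 3.9.4 itself contradicts the protocol baseline. The documents do not establish this. The section opens by averaging replicates per time point and then refers to the last screening measurements in the plural, which can be read as the screening triplicate mean. The two would differ only if the sentence means the last single tracing, or if a later unscheduled screening ECG exists.

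SAP 2.1.8 is a general safety rule and SAP 3.9.4 is specific to ECGs, so a statistician might let the specific section prevail. That is reasonable, but the SAP does not say so, and 2.1.8 names ECGs. The clause in 2.1.8 that takes the last of several values is not part of the problem: it covers only rare cases where the time order is unknown.

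It is also tempting to link this to the QTcF dose rules in protocol Table 6-3. Those are applied after the reading is confirmed at the site, and the SAP baseline does not feed them.

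Finally, baseline noise should be alike in the two randomised arms. It blurs the counts without favouring either arm.

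**Conclusion.** Two inconsistencies stand. First, SAP 3.9.4 describes centrally read replicates at each scheduled time point, while the readable protocol describes locally read ECGs with replicates at screening only. It would go too far to say that central reading never existed: parts of the protocol are blacked out, the ECG rows of Table 7-1 are not visible, and another document may set it up. Second, SAP 2.1.8 selects a different QTcF baseline from SAP 3.9.4 and from the protocol.

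The consequence is confined to descriptive safety tables; no efficacy analysis or hypothesis test is touched. The size is illustrative, because it rests on an assumed SD and independent errors. It lies mainly in the > 30 ms category: for s of 8 to 12 ms, 0.40% to 3.9% false increases per ECG with the single tracing against 0.06% to 1.5% with the triplicate mean. For > 60 ms it stays at or below about 0.02% over that range. The textual conflict between the baseline rules does not depend on those figures.

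**What to change.** - In SAP 3.9.4, name the locally read ECGs recorded in the CRF as the source, with averaging where replicates exist, that is at screening. If central reading was done, cite the document that sets it up instead.
- In SAP 3.9.4, state one QTcF baseline: the mean of the screening triplicate, as in protocol 7.2.2.7.1.
- In SAP 2.1.8, exempt ECGs from the general rule and refer to 3.9.4.
- The protocol sentence on averaging covers QTcF only, so SAP 3.9.4 should also name the baseline visit for PR, QRS and heart rate, and apply it consistently.

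The cost is SAP wording and a derivation in the ECG dataset. No new data are needed for QTcF, because the protocol already has the averaged screening value entered in the CRF.

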3.9.5 Cardiac imaging (MUGA / ECHO)

Note: If there is any change in the methodology used throughout the study compared to baseline, the post-baseline values for which the methodology differs from baseline will be discarded in the tables presenting comparisons to baseline.

For left ventricular ejection fraction (LVEF) a shift table using CTC grades for 'Ejection fraction - decrease' as defined per CTCAE version v4.03 to compare baseline to the worst on-treatment value will be provided.

A listing of patients with newly occurring clinically significant abnormality will be produced by treatment arm.

3.9.6 Other safety data

Other safety data (e.g. data relating to liver events) will be listed in the safety set.

Data from other tests will be listed, notable values will be flagged, and any other information collected will be listed as appropriate.

All assessments collected later than 30 days after the last treatment date will be flagged in the listings.

Any statistical tests performed to explore the data will be used only to identify any interesting comparisons that may warrant further consideration.

[REDACTED]

3.10 Pharmacokinetic (PK) analyses

3.10.1 General principle

All PK analyses for alpelisib and fulvestrant will be based on the PK Analysis set. However, only samples taken within the following time windows around the scheduled time points and at steady state will be used for summary tables and profiles which are summarized by time point:

- Pre-dose: prior to dosing on the assessment day and collected at approximately 24 ± 2 hours after the last dose

- 1 h post-dose: within \pm 10 minutes of the scheduled time point
- 2, 4, 6 or 8 h post-dose: within \pm 30 minutes of the scheduled time point

In addition the following criteria for alpelisib samples considered at steady state must be met:

- assessments with at least 3 continuous days of daily dosing at the planned dose (dose assigned at study entry) prior to the day of alpelisib PK assessment;
- no vomiting occurs within the first 4 hours of the last dose (pre-dose trough samples);
- no vomiting occurs within the first 4 hours of the current and last dose (post-dose sparse samples).

All samples regardless of time window or steady state status will be used for the individual time profile figures.

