6.1.1.2 Fulvestrant dosing

Fulvestrant 500 mg will be given at Cycle 1 Day 1 and 15 after randomization and then at Day 1 of each subsequent cycle during the randomized treatment phase (+/- 3 days). Fulvestrant is administered intramuscularly into the buttocks slowly as two 5mL injections, one in each buttock.

No dose modification is allowed for fulvestrant. Please refer to the local approved prescribing information. Any planned variance from these guidelines in the view of the patient safety must be previously discussed with the Sponsor unless there is an urgent need for action.

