6.1.1.2.1 Additional dosing guidelines for pharmacokinetic sampling

On days with fulvestrant pharmacokinetic sampling (Day 15 of Cycles 1, 2, 4, 6, and 8) the following additional guidelines should be followed: the pre-dose sample should be drawn just before fulvestrant dosing. The sampling time of the pre-dose PK sample and the dosing time of fulvestrant must be precisely recorded in the CRF. Furthermore, the dosing date and time of the previous dose of fulvestrant must be precisely recorded in the CRF.

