1	15	Pre-dose*	302 3021	302	2	401 4011	401	2
1	15	1 h post dose ± 10 min	302	303	2			
1	15	2 h post dose ± 30 min	302	304	2			
1	15	4 h post dose ± 30 min	302	305	2			
1	15	6 h post dose ± 30 min	302	306	2			
1	15	8 h post dose ± 30 min	302	307	2			
2	1	Pre-dose*	303 3031	308	2	402 4021	402	2
4	1	Pre-dose*	304 3041	309	2	403 4031	403	2
6	1	Pre-dose*	305 3051	310	2	404 4041	404	2
8	1	Pre-dose*	306 3061	311	2	405 4051	405	2
Anytime		Unscheduled		3001+	2		4001+	2

* Take sample immediately prior to study treatment dose; at days of PK evaluation oral treatment doses should be taken at the clinical site

+ Refer to Lab manual for naming conventions

§ Four digit dose reference ID for pre-dose and 24h post dose samples ending on 1 refers to the dose taken before the PK sample (last dose information)

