3.10.2 PK concentrations

Trough PK concentrations of alpelisib and fulvestrant will be summarized by visit and treatment group. Alpelisib sparse PK concentrations will be reported at Cycle 1 Day 15.

Descriptive statistics of concentrations will be provided using steady state concentrations only and include n, number of non-zero concentrations, arithmetic mean, geometric mean, median, SD, coefficient of variation CV (%), geometric CV (%), minimum and maximum. Coefficient of variation CV (%) is calculated as follows from non-zero values: $100 * (\text{SD}/\text{arithmetic mean})$.

Geometric CV (%) is calculated as follows from non-zero values:

[figure not shown]
[figure not shown]
$$\text{CV}(\%) = 100 \cdot \sqrt{\exp(\hat{\sigma}^2) - 1}$$

where $\hat{\sigma}^2$ denotes the variance of the log-transformed values.

Geometric mean and arithmetic mean (SD) plots will also be graphically presented for trough concentration-time data. Individual concentration-time profiles will be displayed graphically for trough concentrations (alpelisib and fulvestrant) and sparse concentrations (alpelisib only) separately. All PK concentration data will be listed as appropriate.

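### SAP 3.10.1 applies one pre-dose window, about 24 ± 2 h after the last dose, to both drugs; no scheduled fulvestrant trough, taken 14 or 28 days after the previous injection, can meet it

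*SAP*

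**What the plan says.** SAP 3.10.1 opens by covering both drugs: "All PK analyses for alpelisib and fulvestrant will be based on the PK Analysis set. However, only samples taken within the following time windows" and at steady state enter the summary tables and by-time-point profiles. The pre-dose entry in that list is "Pre-dose: prior to dosing on the assessment day and collected at approximately 24 ± 2 hours after the last dose". It names no drug. The next rule does name one: "In addition the following criteria for alpelisib samples considered at steady state must be met". The readable SAP gives no fulvestrant window and no fulvestrant steady-state criterion.

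SAP 3.10.2 then plans the outputs: "Trough PK concentrations of alpelisib and fulvestrant will be summarized by visit and treatment group", with mean plots of the trough data, and "Descriptive statistics of concentrations will be provided using steady state concentrations only".

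Protocol 6.1.1.2 sets the injection schedule: "Fulvestrant 500 mg will be given at Cycle 1 Day 1 and 15 after randomization and then at Day 1 of each subsequent cycle", with a 3-day allowance either way. Tables 7-6 and 7-7 sample fulvestrant only before dosing: at C1D15, C2D1, C4D1, C6D1 and C8D1 in the sparse subset of about 200 patients, and at C6D1 alone in all others.

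**The concern.** A window of about one day after the last dose describes a drug taken daily. Fulvestrant is given every two weeks at first and every four weeks afterwards. If the window is applied to fulvestrant as the section's opening sentence directs, it does not trim outlying samples. It excludes all of them.

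Fulvestrant PK in the combination is a secondary objective, and protocol 1.2.4.2 and 7.2.3.2 say the troughs serve to assess the effect of alpelisib on fulvestrant. A programmer who follows the SAP produces empty fulvestrant tables and mean plots. One who avoids that result must invent an inclusion rule that is documented nowhere in the readable plan.

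**Working it through.** **Inputs.** Window: 24 ± 2 h, i.e. 22 to 26 h (SAP 3.10.1). Cycle: 28 days (SAP 2.1.6). Injections: C1D1, C1D15, then Day 1 of each cycle (protocol 6.1.1.2). Fulvestrant samples: Tables 7-6 and 7-7. Alpelisib: once daily.

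**Formulas.** Study day = (cycle − 1) × 28 + day. Gap in hours = (sample day − day of previous injection) × 24.

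**The plan's own figure.** For once-daily alpelisib the gap is 24 h, inside 22 to 26 h. The window reproduces for that drug.

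**Fulvestrant.**

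| Sample | Study day | Previous injection | Gap | Gap with ±3 days | Within 22–26 h |
|---|---|---|---|---|---|
| C1D15 | 15 | Day 1 | 14 d = 336 h | 264–408 h | No |
| C2D1 | 29 | Day 15 | 14 d = 336 h | 264–408 h | No |
| C4D1 | 85 | Day 57 | 28 d = 672 h | 600–744 h | No |
| C6D1 | 141 | Day 113 | 28 d = 672 h | 600–744 h | No |
| C8D1 | 197 | Day 169 | 28 d = 672 h | 600–744 h | No |

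Result: 0 of 5 in the sparse subset, and 0 of 1 (C6D1) in other patients.

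**Stress test.** Stack every tolerance that could be argued: injection ±3 days, visit ±3 days, sample ±1 day, giving ±7 days. The shortest gap is then (14 − 7) × 24 = 168 h, and 168 / 26 is about 6.5 times the upper limit. The count stays at zero.

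**Alternative sampling days.** Protocol 6.1.1.2.1 lists fulvestrant sampling on Day 15 of Cycles 1, 2, 4, 6 and 8, which disagrees with Tables 7-6 and 7-7 from Cycle 2 on. On that list every gap is 14 d = 336 h, again 0 of 5.

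**Steady state.** Injections given before each sample: C1D15 1, C2D1 2, C4D1 4, C6D1 6, C8D1 8. Protocol 7.2.3.2 puts full steady state after 6 administrations, so C6D1 and C8D1 qualify (2 of 5). Protocol 1.2.1.1 puts it within the first month for the same regimen, which would admit roughly C2D1 onward (4 of 5). The SAP adopts neither. Either way, restricting every summary to steady state removes early visits from the display, although protocol 10.5.5.1 plans to describe the time course towards steady state.

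**The case against.** The best defence is that the SAP does not say whose last dose is meant. In Tables 7-6 and 7-7 every scheduled fulvestrant sample is drawn alongside an alpelisib/placebo pre-dose sample, about 24 h after the previous tablet and in both arms. Read as time since the last alpelisib/placebo dose, the window can be met and the tables are not empty.

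That reading is possible but does not rescue the rule. The SAP does not state it. Protocol 6.1.1.2.1 anchors a fulvestrant sample to the earlier fulvestrant injection: "Furthermore, the dosing date and time of the previous dose of fulvestrant must be precisely recorded in the CRF". The fulvestrant columns of Tables 7-6 and 7-7 also carry their own dose identifiers; the footnote explains that the four-digit form "refers to the dose taken before the PK sample (last dose information". Protocol 6.3.1.2, Table 6-3 and 7.1.3 let fulvestrant continue while alpelisib/placebo is held or after it is stopped. Under the alpelisib reading, fulvestrant troughs would therefore be dropped because of events on the other drug, and nothing would limit the time since the injection.

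A second objection is that little depends on this. That largely stands. The outputs are descriptive, population PK goes to a separate report, table shells and programming specifications are separate documents not seen here, and an empty table would be noticed. The window was probably meant for alpelisib alone.

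Three stronger inferences are not supported:

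- **That the between-arm fulvestrant comparison is lost.** Text beside it in protocol 10.5.5.1 is redacted, as is SAP text between 3.10.3 and 3.10.5, so the data it uses cannot be confirmed.
- **That only 2 of 5 visits count as steady state.** This relies on one of two conflicting protocol statements.
- **That ±6 days (8–20 or 22–34 days) is the natural fulvestrant tolerance.** It adds 3 days at both ends. C1D1 is the randomization day (protocol 7.1) and does not carry that shift, and protocol 2.3 and 6.1.1 define the cycle as 28 ± 3 days.

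**Conclusion.** The rule is wrong as written; this is more than missing detail. Measured from the previous fulvestrant injection, none of the scheduled fulvestrant troughs can enter the SAP 3.10.2 summaries or mean plots: 0 of 5 time points in the sparse subset and 0 of 1 elsewhere. This rests on taking the last dose to be that of the drug being measured, which is how the protocol records it. The count does not depend on which visit tolerance or which version of the sampling days is used.

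The effect is limited to descriptive secondary PK outputs. All samples remain in the individual profiles and listings, and no efficacy analysis is touched. The point is worth correcting because the summaries bear on a stated secondary objective and the remedy is small.

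**What to change.** In SAP 3.10.1 and 3.10.2:

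1. Limit the 24 ± 2 h pre-dose window to alpelisib.
2. For fulvestrant, include samples drawn before that visit's injection whose time since the previous fulvestrant injection lies within one stated tolerance of the scheduled 14 or 28 days. A tolerance of ±3 days (11–17 or 25–31 days) matches the dosing window and the 28 ± 3 day cycle definition. Protocol 7.1 and 7.2.3.3.1 set separate allowances for the sampling day (none for sparse samples, ±1 day for others), so the SAP should state which tolerance governs.
3. Define fulvestrant steady state, after reconciling protocol 7.2.3.2 with 1.2.1.1.
4. Exempt the by-visit fulvestrant time-course display planned in protocol 10.5.5.1 from the steady-state restriction, so that C1D15, C2D1 and C4D1 remain visible.

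Separately, reconcile the fulvestrant sampling days in protocol 6.1.1.2.1 with Tables 7-6 and 7-7. This does not alter the result above.

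The cost is a few SAP sentences and the protocol wording reconciliations in item 3 and the last point. No new data are needed, because the CRF already captures the previous fulvestrant dose date and time.
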